**11. What time of mobile do you have?**

- iPhone
- Android

**12. If you have an iPhone, what model do you have?**

- iPhone 7 or above
- iPhone 6, iPhone 6+, iPhone 6s, iPhone 6S Plus
- iPhone 5, iPhone 5c, iPhone 5s
- iPhone 4s

**13. What is your current mobile provider?**

- Verizon Wireless
- AT&T
- T-Mobile USA
- Sprint Nextel
- U.S. Cellular
- Other: \_\_\_\_\_

**You have reached the end of the survey. Please click “Finish” to submit your survey responses.**

## 15.3 Baseline Survey

### My Digital Study Baseline Survey

We want you to consider the information collected on this form to be private. We will keep it confidential and only use it to contact for this study.

In order to ensure that the data collected is useful and complies with the Western Institutional Review Board (WIRB) guidelines, all study participants must meet certain requirements.

**Welcome to the Baseline Survey!**

**7. What is your birth date (MM/DD/YYYY)?**

DOB: \_\_\_\_ / \_\_\_\_ / \_\_\_\_

**8. Please specify your gender:**

- MALE
- FEMALE

**9. Please specify your race / ethnicity:**

- White
- Hispanic/Latino
- Black or African American
- Native American or American Indian
- Asian / Pacific Islander
- Other: \_\_\_\_\_
- Prefer not to answer (?)

**10. A family may be described as “adults and children who live together most of the time and share their income.” Using this definition, how many people (including yourself) are in your family?**

- 1
- 2
- 3
- 4
- 5
- 6
- 7
- 8
- 9
- 10

**11. Please describe your family's annual income level:**

- Less than \$20,000
- \$55,000 - \$100,000
- \$20,000 to \$55,000
- Over \$100,000

**12. If you have a spouse or romantic partner who lives with you, does he/she smoke cigarettes regularly?**

- No
- Yes
- I have no spouse or romantic
- My spouse or romantic partner does not live with me

**13. What is the highest level of education that you completed?**

- Did not graduate from high school and did not get GED
- Graduated high school
- Received a GED
- Some college
- Associate degree
- Bachelor's degree
- Some graduate school
- Master's degree
- Professional degree (e.g., PhD, MD or JD)

**14. How old were you when you started smoking?**

Smoking onset age: \_\_\_\_\_

**15. How long have you been a regular smoker?**

- Less than 2 years       6-10 years
- 2-5 years       More than 10 years

**16. Have you previously tried to quit smoking?**

- YES
- NO

**17. If Yes, how many times have you previously tried to quit smoking?**

- YES
- NO

**18. What was your longest duration without smoking?**

- Less than a week       1 month – 6 months       More than 1 year
- 1 week – 1 month       6 months – 1 year

**19. How soon after you wake do you smoke your first cigarette?**

- Within 5 minutes       31 to 60 minutes
- 6 to 30 minutes       After 60 minutes

**20. Do you find it difficult to refrain from smoking in places where it is forbidden? (e.g., in church, at the library, in the cinema)?**

- YES
- NO

**21. Which cigarette would you hate to give up?**

- The first in the morning
- Any other

**22. How many cigarettes per day do you smoke?**

- 10 or less       21 to 30
- 11 to 20       31 or more

**23. Do you smoke more frequently during the first hours after waking than during the rest of the day?**

YES  
 NO

**24. Do you smoke when you are so ill that you are in bed most of the day?**

YES  
 NO

**25. In the last week, approximately how much money have you spent buying cigarettes?**

Less than \$15       \$31-\$50  
 \$16-\$30       More than \$50

**26. Within the past 30 days about how often do you use the internet?**

At least several times per day  
 At least once per day but less than several times per day  
 At least once per week but less than once per day  
 At least once in past month but less than once per week

**Medical History:**

**27. Please enter your height and weight:**

Height: \_\_\_\_\_ Weight: \_\_\_\_\_

**28. Please indicate how strongly you agree with this statement: "I generally feel sad or depressed".**

Never     Rarely     Sometimes     Often     Very often     Always

**29. Please indicate if you have ever been diagnosed by a doctor with any of the following conditions:**

**Pulmonary:**

|   | YES | NO | Not sure |
|---|-----|----|----------|
| Emphysema / Chronic Obstructive Pulmonary Disease |     |    |          |
| Asthma  |     |    |          |
| Other lung or breathing condition                 |     |    |          |

**Cardiac:**

|  | YES | NO | Not sure |
|--|------------|-----------|-----------------|
| Coronary artery disease (blockade of heart arteries) |            |           |                 |
| Heart attack   |            |           |                 |
| High blood pressure                                  |            |           |                 |
| Congestive heart failure                             |            |           |                 |
| Other heart conditions                               |            |           |                 |

**Neurologic:**

|                                      | YES | NO | Not sure |
|--------------------------------------|------------|-----------|-----------------|
| Stroke                               |            |           |                 |
| Epilepsy                             |            |           |                 |
| Migraine or chronic headaches        |            |           |                 |
| Multiple sclerosis                   |            |           |                 |
| Traumatic Brain Injury               |            |           |                 |
| Chronic pain                         |            |           |                 |
| Other brain or spinal cord condition |            |           |                 |

**Metabolic:**

|                                   | YES | NO | Not sure |
|-----------------------------------|------------|-----------|-----------------|
| Diabetes                          |            |           |                 |
| High cholesterol or triglycerides |            |           |                 |
| Thyroid condition                 |            |           |                 |
| Other metabolic condition         |            |           |                 |

**Cancer:**

|                        | YES | NO | Not sure |
|------------------------|------------|-----------|-----------------|
| Lung Cancer            |            |           |                 |
| Breast Cancer          |            |           |                 |
| Colon Cancer           |            |           |                 |
| Other Malignant Cancer |            |           |                 |

**Mental Health:**

|  | YES | NO | Not sure |
|--|------------|-----------|-----------------|
| Depression                                       |            |           |                 |
| Anxiety disorder                                 |            |           |                 |
| Schizophrenia                                    |            |           |                 |
| Hospitalization for mental or emotional problems |            |           |                 |
| Other mental or emotional disorder               |            |           |                 |

**30. Please answer these smoking-related questions to the best of your ability**

|                                    | Not at all | Very Little | A Little | Moderately | A lot | Quite a lot | Extremely |
|------------------------------------|-------------------|--------------------|-----------------|-------------------|--------------|--------------------|------------------|
| Do you find cigarettes satisfying? | 1                 | 2                  | 3               | 4                 | 5            | 6                  | 7                |
| Do cigarettes taste good to you?   | 1                 | 2                  | 3               | 4                 | 5            | 6                  | 7                |

|   |                   |                    |                 |                   |              |                    |                  |  |
|---|-------------------|--------------------|-----------------|-------------------|--------------|--------------------|------------------|--|
| Do you enjoy smoking cigarettes?                      | 1                 | 2                  | 3               | 4                 | 5            | 6                  | 7                |  |
|   | Not at all | Very Little | A Little | Moderately | A lot | Quite a lot | Extremely |  |
| Does smoking cigarettes calm you down?                | 1                 | 2                  | 3               | 4                 | 5            | 6                  | 7                |  |
| Does smoking cigarettes make you feel more awake?     | 1                 | 2                  | 3               | 4                 | 5            | 6                  | 7                |  |
| Does smoking cigarettes make you feel more irritable? | 1                 | 2                  | 3               | 4                 | 5            | 6                  | 7                |  |
| Does smoking cigarettes help you concentrate?         | 1                 | 2                  | 3               | 4                 | 5            | 6                  | 7                |  |
| Does smoking cigarettes reduce your hunger for food?  | 1                 | 2                  | 3               | 4                 | 5            | 6                  | 7                |  |

|  |                   |                    |                 |                   |              |                    |                  |
|--|-------------------|--------------------|-----------------|-------------------|--------------|--------------------|------------------|
|  | Not at all | Very Little | A Little | Moderately | A lot | Quite a lot | Extremely |
| Does smoking cigarettes make you less dizzy? | 1                 | 2                  | 3               | 4                 | 5            | 6                  | 7                |
| Does smoking cigarettes make you nauseous?   | 1                 | 2                  | 3               | 4                 | 5            | 6                  | 7                |

|  |                   |                    |                 |                   |              |                    |                  |
|--|-------------------|--------------------|-----------------|-------------------|--------------|--------------------|------------------|
|  | Not at all | Very Little | A Little | Moderately | A lot | Quite a lot | Extremely |
| Do you enjoy the sensation in your throat and chest when you smoke cigarettes? | 1                 | 2                  | 3               | 4                 | 5            | 6                  | 7                |
|  | Not at all | Very Little | A Little | Moderately | A lot | Quite a lot | Extremely |

|   |   |   |   |   |   |   |   |
|---|---|---|---|---|---|---|---|
| Does smoking cigarettes immediately relieve your craving for a cigarette? | 1 | 2 | 3 | 4 | 5 | 6 | 7 |
|---|---|---|---|---|---|---|---|

|  | Not at all | Very Little | A Little | Moderately | A lot | Quite a lot | Extremely |
|--|------------|-------------|----------|------------|-------|-------------|-----------|
| I believe a mobile solution will help me to achieve my goal of becoming smoke-free | 1          | 2           | 3        | 4          | 5     | 6           | 7         |
| I am extremely confident that I will be able to quit this time.                    | 1          | 2           | 3        | 4          | 5     | 6           | 7         |
| I would be attempting to quit even without participating in this study.            | 1          | 2           | 3        | 4          | 5     | 6           | 7         |
| I believe that a financial reward would help me quit smoking.                      | 1          | 2           | 3        | 4          | 5     | 6           | 7         |

**31. Please indicate how strongly you agree with these statements**

Please show for each of the items below how you have been feeling over the past week?

|                    | Not at all | Very Little | A Little | Moderately | A lot | Quite a lot | Extremely |
|--------------------|------------|-------------|----------|------------|-------|-------------|-----------|
| Depressed          | 1          | 2           | 3        | 4          | 5     | 6           | 7         |
| Anxious            | 1          | 2           | 3        | 4          | 5     | 6           | 7         |
| Irritable          | 1          | 2           | 3        | 4          | 5     | 6           | 7         |
| Restless           | 1          | 2           | 3        | 4          | 5     | 6           | 7         |
| Hungry             | 1          | 2           | 3        | 4          | 5     | 6           | 7         |
| Poor Concentration | 1          | 2           | 3        | 4          | 5     | 6           | 7         |

|                     |   |   |   |   |   |   |   |
|---------------------|---|---|---|---|---|---|---|
| Poor Sleep at Night | 1 | 2 | 3 | 4 | 5 | 6 | 7 |
|---------------------|---|---|---|---|---|---|---|

How much of the time have you felt the urge to smoke in the past week? (Circle one number)

| Not at all | A little of the time | Some of the time | A lot of the time | Almost all the time | All of the time |
|------------|----------------------|------------------|-------------------|---------------------|-----------------|
| 0          | 1                    | 2                | 3                 | 4                   | 5               |

How strong have the urges been? (Circle one number)

| No urges | Slight | Moderate | Strong | Very Strong | Extremely Strong |
|----------|--------|----------|--------|-------------|------------------|
| 0        | 1      | 2        | 3      | 4           | 5                |

Have you experienced any of the following over the past week? (Circle one number for each item)

|                     | No | Slight | Moderate | Severe | Very Severe |
|---------------------|----|--------|----------|--------|-------------|
| Sores in the mouth  | 1  | 2      | 3        | 4      | 5           |
| Constipation        | 1  | 2      | 3        | 4      | 5           |
| Cough / Sore Throat | 1  | 2      | 3        | 4      | 5           |

**You have reached the end of the survey. Please click “Finish” to submit your survey responses.**

## 15.4      Outcome Survey

### My Digital Study Outcome Survey

We want you to consider the information collected on this form to be private. We will keep it confidential and only use it to contact for this study.

Welcome to the Outcome Survey! Please answer these questions to the best of your ability.

**1. Have you smoked (even a puff) in the last 30 days?**

- YES
- NO

**2. If YES, have you smoked (even a puff) in the last 14 days?**

- YES
- NO

**3. If YES, have you smoked (even a puff) in the last 7 days?**

- YES
- NO

*~~ If the answer is “YES” to any of the questions 1-3, users will be prompted to Fagerstrom Test (Questions 4-9) for Nicotine Dependence*

**4. How soon after you wake do you smoke your first cigarette?**

- Within 5 minutes       31 to 60 minutes
- 6 to 30 minutes       After 60 minutes

**5. Do you find it difficult to refrain from smoking in places where it is forbidden? (e.g., in church, at the library, in the cinema)?**

- YES
- NO

**6. Which cigarette would you hate to give up?**

- The first in the morning
- Any other

**7. How many cigarettes per day do you smoke?**

- 10 or less       21 to 30

11 to 20       31 or more

**8. Do you smoke more frequently during the first hours after waking than during the rest of the day?**

YES  
 NO

**9. Do you smoke when you are so ill that you are in bed most of the day?**

YES  
 NO

**10. Are you currently taking any quit aids (ex. Nicotine Replacement Therapies (NRT) like nicotine gum, nicotine lozenges, nicotine patches, nicotine nasal spray / inhalers, or something similar) or medication (ex. Chantix, Zyban, or something similar) to help you quit smoking? ~ If the answer is "YES", users will be prompted to complete Questions 11-16**

YES  
 NO

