## **6.4 Permitted Concomitant Treatments**

To control for medication or NRT use, participants will not be eligible to enroll if they are currently using a medication or NRT at study enrollment.

Starting at Day 0 of the study, study participants will be allowed to choose to begin using a smoking cessation medication or NRT. Participants will be asked about medication or NRT use during the study in outcome survey.

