**Outcome Survey:**

- Link to survey will be sent via email and SMS
- After a participant completes the outcome survey a linked CO assessment reminder will be automated.
- Participants will report any smoking cessation medication or NRT use

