### **11. QUALITY CONTROL AND QUALITY ASSURANCE**

#### **11.1 Data Collection**

Data collection during the 8-week study will occur through the Baseline Survey, Smokerlyzer Confirmation (Day 28), the Outcome Survey at 8 weeks and the iCO Smokerlyzer assessment.

Primary outcome data, including covariates to be included in regression analyses, are acquired via the web-based baseline survey and outcome survey. Data are conveyed via an automated process from the web-based survey into a format matching the study database. Research coordinator is responsible for entering the survey data into the study database within 72 hours of survey completion.

Secondary outcome data: 1) CO readings are automatically conveyed via email by the iCO Smokerlyzer App to the study coordinator, who will enter the result into the database (a numerical value in parts-per-million (ppm; <7 ppm is defined as evidence of cigarette abstinence); 2) self-reported NRT and smoking cessation pharmacotherapy use (including e- cigarette use) will be acquired via the outcome survey.

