**11. Please check which quit aid(s) you are currently using:**

Nicotine gum  
 Nicotine lozenge  
 Nicotine patch  
 Nicotine nasal spray  
 Nicotine inhaler  
 Chantix® (Varenicline)  
 Zyban® or Wellbutrin® (Bupropion)  
 Other (please specify): \_\_\_\_\_

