**12. Do you ever forget to use your medicine / NRT?**

YES  
 NO

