Primary outcome data, including covariates to be included in regression analyses, are acquired via the web-based baseline survey and outcome survey. Data are conveyed via an automated process from the web-based survey into a format matching the study database. Research coordinator is responsible for entering the survey data into the study database within 72 hours of survey completion.

Secondary outcome data: 1) CO readings are automatically conveyed via email by the iCO Smokerlyzer App to the study coordinator, who will enter the result into the database (a numerical value in parts-per-million (ppm; <8 ppm is defined as evidence of cigarette abstinence); 2) self-reported NRT and smoking cessation pharmacotherapy use (including e-cigarette use) will be acquired via the outcome survey.

Data Analysis Plan:

[name], will conduct all study analyses after the study database is locked. All analyses will be performed on the intent-to-treat (ITT) population, with non-response imputed as continued smoking. 30-day smoking cessation status (dichotomous variable: yes/no) will be compared between the CKT and QuitGuide groups utilizing logistic regression. Two-sided p-values will be calculated from logistic regression models, with adjustments to the models by: race, education, nicotine dependence, and living with a partner who smokes, consistent with previous studies' models.

Concordance rates between self-reported 30-day abstinence and the remote CO monitoring result will be estimated, with concordance > 85% considered evidence of a valid reporting process by Magellan Behavioral Health. Concordance rates between the video-monitored and unmonitored groups will be compared to determine the value of video monitoring the CO assessment.

Secondary analysis of the subgroup of NRT/pharmacotherapy users will be conducted to compare cessation rates between the CKT+NRT group and the CKT-only group, to confirm the initial trial result that CKT+NRT is not superior to CKT-alone.

Quality Assurance

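### The outcome survey records only current quit-aid use, and the CKT+NRT versus CKT-only comparison is too imprecise to confirm that adding NRT is not superior

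*Protocol*

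**What the plan says.** **When use may start.** Protocol 6.4: "Starting at Day 0 of the study, study participants will be allowed to choose to begin using a smoking cessation medication or NRT".

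**What the survey is said to collect.** Protocol 6.4: "Participants will be asked about medication or NRT use during the study in outcome survey". Protocol 7.10, under Outcome Survey: "Participants will report any smoking cessation medication or NRT use".

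**What the survey asks.** Protocol 15.4, question 10: "Are you currently taking any quit aids". Only a yes opens questions 11–16. Question 11: "Please check which quit aid(s) you are currently using". Questions 12–15 are present-tense adherence items, such as "Do you ever forget to use your medicine / NRT". The survey window is Day 53–59 (protocol 7.10).

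**Source of the data.** Protocol 11.1: "self-reported NRT and smoking cessation pharmacotherapy use (including e- cigarette use) will be acquired via the outcome survey". The SAP, under Data Acquisition, says the same: "self-reported NRT and smoking cessation pharmacotherapy use (including e-cigarette use) will be acquired via the outcome survey". The Week 4 check (protocol 7.9, 8.1) concerns the CO submission, recorded as yes or no, and does not ask about quit aids.

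**Use of the data.** Protocol 2.2 makes the comparison of cessation rates between CKT+NRT and CKT-only a secondary objective. Protocol 10.4 and the SAP (10.4, Data Analysis Plan) repeat it. The stated purpose is to confirm what the sponsor's initial trial is said to have shown, namely that the combination is not superior. None of these sections defines the CKT+NRT group or gives a test, margin or decision rule. All analyses are ITT (protocol 10.1), and the SAP Data Analysis Plan counts non-responders as still smoking.

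**The concern.** There are two separate problems.

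**Exposure is measured at one time point.** Someone who used a patch in weeks 1–5 and then stopped answers no to question 10, skips questions 11–16, and leaves no trace of use. The exposure error runs one way, with users appearing as non-users. The resulting bias in the quit-rate difference can take either sign, because it depends on whether quitters or continuing smokers stop their quit aid more often. Survey non-responders add to this: they have an imputed outcome but no NRT status, and no text says which group they join.

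**The stated purpose is stronger than the comparison can bear.** NRT use is chosen by the participant, the comparison sits inside one arm, and nothing is prespecified that would turn a result into evidence of non-superiority. As worded, a non-significant difference is likely to be read as the hoped-for confirmation.

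**Working it through.** **Inputs from the documents.** CKT arm 78 (protocol 10.5). Pilot retention 87.7% and completer 30-day abstinence 29.9% (protocol 1.3). ITT abstinence 26.2% (protocol 10.5).

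**Assumptions.** NRT uptake, stopping rates and quit rates by NRT use are not given in the documents. Uptake is taken as 20–40%, with 30% as base case.

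**The plan's own figure.** None is given for this comparison. The primary sample size reproduces: 26.2% vs 8.3%, two-sided 0.05 and 85% power give 79 per group by the pooled-variance formula, against 78 stated. Power at 78 is 84.8%.

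**Bias from asking about current use.** Responders N = 78 × 0.877 = 68.41. Let u be uptake, q the quit rate in users and non-users alike (no true difference), and sQ, sS the shares of quitting and smoking users who stopped before the survey.

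- Observed CKT+NRT rate = q(1−sQ) / [q(1−sQ) + (1−q)(1−sS)]
- Observed CKT-only rate = [(1−u)q + u·q·sQ] / [(1−u) + u·q·sQ + u(1−q)sS]

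With u = 0.30 and q = 0.299 there are 20.52 users (6.14 quit) and 47.88 non-users (14.32 quit).

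| Stopped: quitters / smokers | CKT+NRT | CKT-only | Difference | Range for 20–40% uptake |
|---|---|---|---|---|
| 20% / 20% | 29.9% | 29.9% | 0.0 | 0.0 |
| 20% / 10% | 4.91/17.86 = 27.5% | 15.54/50.55 = 30.8% | −3.3 | −2.9 to −3.7 |
| 20% / 30% | 4.91/14.98 = 32.8% | 15.54/53.43 = 29.1% | +3.7 | +3.4 to +4.1 |
| 40% / 20% | 3.68/15.19 = 24.2% | 16.77/53.22 = 31.5% | −7.3 | −6.6 to −8.0 |
| 20% / 40% | 4.91/13.54 = 36.3% | 15.54/54.87 = 28.3% | +7.9 | +7.3 to +8.6 |

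Shifts of −16.5 or +19.1 points need extreme patterns (50%/0% or 20%/60%).

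**Placement of non-responders.** 78 − 68.41 = 9.59, counted as smokers, with no true difference among responders and 30% uptake:

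- In CKT-only: 14.32/(47.88 + 9.59) = 24.9%, against 29.9%; difference +5.0 (+4.5 to +5.7 for 20–40% uptake).
- In CKT+NRT: 6.14/(20.52 + 9.59) = 20.4%, against 29.9%; difference −9.5 (−12.3 to −7.8).

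**Precision with perfect classification.** Half-width = 1.96·√[p(1−p)(1/a + 1/b)]. For 20 vs 48: 1.96·√[0.299 × 0.701 × (1/20 + 1/48)] = 0.239. Power is by exact enumeration of the two-sided pooled score test at 0.05.

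| Sample and uptake | Split | Half-width (points) | Power, +10 points | Power, +20 points |
|---|---|---|---|---|
| 68 responders, 20% | 14 vs 54 | 27 | 12% | 30% |
| 68 responders, 30% | 20 vs 48 | 24 | 14% | 37% |
| 68 responders, 40% | 27 vs 41 | 22 | 14% | 39% |
| All 78, 30% (p = 26.2%) | 23 vs 55 | 21 | 15% | 40% |

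For scale, excluding a 10-point advantage with 80% power, one-sided 0.025 and equal true rates of 26.2%, needs (1.96 + 0.842)² × 2 × 0.262 × 0.738 / 0.10² ≈ 304 per group.

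**The case against.** **The promise of any-time use is an interpretation.** The sentence in 6.4 could mean that the question is put during the study. The word any in 7.10 has no time frame and could mean any product. Protocol 7.9 expects participants to continue their medication or NRT at Week 4, so current use at Week 8 may have been the intended exposure, and the present tense suits the adherence items that question 10 gates. This stands as a limit on certainty. Against it, 6.4 places the question in the outcome survey itself, and 2.2 speaks of use expected during the trial. If current use was intended, the plan still does not say so.

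**Other records might exist.** Protocol 11.1 and the SAP name the survey without calling it the sole source, and protocol 1.2 says Clickotine helps users track quit-aid use. No section makes app records study data.

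**The demonstrated effect of the wording is small.** All the rates are assumed, and at a 10-point stopping difference the bias is 3 to 4 points beside a half-width of about 24. This stands: better wording alone would not make the comparison confirmatory.

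**This is a subgroup analysis in what the SAP calls a feasibility study.** That limits the weight, but the comparison is a stated secondary objective with a stated conclusion to be confirmed.

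**Stronger readings that the documents do not support.** A reader might infer that the plan assigns early stoppers to CKT-only. No section does; it follows only because nothing on record could place them elsewhere. A reader might also infer that the survey wording would reverse a real NRT effect. With assumed true rates of 40% vs 20% and 30% uptake, 20% stopping in both groups still gives +18.4. A reversal (−1.3) appears only if half the quitters and none of the smokers stop.

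**Conclusion.** The point holds in two parts of unequal weight.

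1. **The purpose (more weight).** A self-selected comparison within at most 78 CKT participants, without a margin or decision rule, cannot confirm that CKT+NRT is not superior. Even with perfect classification, a true 20-point advantage would be missed more often than found in every split examined. This depends on the assumed 20–40% uptake, but not on any assumption about stopping.
2. **The survey item (less weight).** Questions 10–11 do not collect what 6.4 and 7.10 most naturally promise. The bias has no fixed sign, is modest under moderate differential stopping, and rests wholly on assumed rates. The unstated placement of non-responders can move the result by a similar or larger amount.

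The primary CKT versus QuitGuide model does not use NRT status, so nothing here bears on it.

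**What to change.** **Survey.** Reword question 10 to ask about use at any time since the study app was installed, with approximate start and stop dates, and question 11 to match. Add an explicit e-cigarette option, since protocol 11.1 and the SAP say that such use is collected and the present items leave it to the free-text category. Keep the present item on current use as a follow-up and as the gate to questions 12–16.

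**SAP.** Define CKT+NRT as any use from Day 0 to the survey and say whether e-cigarettes count. Because any use puts brief and sustained users together, add current use as a sensitivity analysis. State that the comparison is made in survey responders, as an explicit exception to the all-ITT rule. Report the number of non-responders, with sensitivity analyses placing them, as smokers, in either group.

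**Purpose.** In protocol 2.2 and 10.4 and in the SAP, replace the aim of confirming non-superiority with a descriptive difference and its 95% CI, described as non-randomised.

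**Cost.** A slightly longer survey, dates that rely on 8-week recall, and a wording change to protocol and SAP. Protocol 12.1 requires the funder's prior approval for significant protocol changes, so that step may be needed. No extra participants or visits are required.
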